### **6.6.Statistical Tests**

The default significant level will be 5%; confidence intervals (CIs) will be 95% and all tests will be two-sided, unless otherwise specified in the description of the analyses.

## 6.7. Values below or Above the Quantification Limit

- ADA against efgartigimod: titer of positive ADA samples reported as "negative titer" will be imputed by 1. Listings will always present "negative titer".
- Safety and PD values expressed as below (or above) the quantification limit will be imputed by the
  value of the quantification limit itself. For participants with a baseline PD value below/above the
  quantification limit, the PD parameter will be excluded from the statistical analyses involving
  change and percent change from baseline. Listings will always show the non-imputed values.
- Pharmacokinetic concentrations below the lower quantification limit will be reported in the listings as BLQ. For descriptive statistical analysis, all BLQ values will be set to zero. Listings will always present BLQ.

### 6.8. Common Calculations

For quantitative measurements, change from baseline will be calculated as:

 $\circ$  Change from baseline at Visit X = Value at Visit X – baseline value.

A percent change from baseline can be calculated as;

• Percent change from baseline at Visit X = (actual value at Visit X -baseline value) \*100/baseline value.

## 6.9. Software Version

All analyses will be conducted using SAS version 9.4 or higher.

Document: BIOSdata\argenx\Efgartigimod\HAB40220\Biostatistics\Documentation\SAP

Author: Version Number: 1.0

Version Date: 03 June 2024

Template No.: CS\_TP\_BS016 Revision 7 Reference: CS\_WI\_BS005

Page 24 of 54

## 7. STATISTICAL CONSIDERATIONS

## 7.1. Missing Data

For imputation of missing values related safety, see appropriate section of the applicable endpoints. Other missing values will not be imputed.

## 7.2. Output Presentation

For continuous variables, full descriptive statistics will only be presented if there are at least 2 non-missing observations. Alternatively, only the number of non-missing data points and mean are shown. In tables by analysis visit, only analysis visits with at least 10 participants (overall) will be shown.

Descriptive statistics for safety and efficacy will include the number of non-missing data points, the arithmetic mean, the standard deviation (SD), the median, minimum, Q1, Q3, maximum, and for efficacy the standard error (SE) and 95% CI may be provided in addition (refer to output templates for details).

Mean, Q1, Q3 and median will be presented with one more decimal place than the measured values. SE and SD will be presented with two more decimal places than the measured values. Minimum and maximum will be presented with the same number of decimal places as the measured values.

Descriptive statistics for PD parameters will include the number of non-missing data points, the arithmetic mean, the SD, the SE, the 95% CI, the median, minimum, Q1, Q3, and maximum. Descriptive statistics of total IgG levels will be presented in  $\mu g/mL$ .

Descriptive statistics for PK serum concentrations will include the number of observed values, arithmetic mean, SD, median, minimum and maximum, CV%, the GM, and geometric CV%. Serum concentrations will be reported as received by the bioanalytical laboratory.

Descriptive statistics for PK concentrations will be presented with 3 significant digits in  $\mu$ g/mL for efgartigimod (where appropriate), except values  $\geq$ 1000 which will be presented without the decimals and rounded to the nearest integer. If at least one BLQ value is reported at a specific time point, the GM and geometric CV% for that time point will not be calculated. In addition, if more than half of the values per time point are BLQ, the arithmetic mean will be reported as BLQ and SD, CV%, GM, and geometric CV% will not be calculated.

Descriptive statistics for immunogenicity titer values will include the number of observed values, arithmetic mean, SE, 95% CI, median, Q1, Q3, minimum, maximum, the GM, and geometric CV%.

For event-type safety data, the number and percentage of participants with an event will be shown. The denominator will be all participants in the analysis set per treatment.

Document: BIOSdata\argenx\Efgartigimod\HAB40220\Biostatistics\Documentation\SAP

Author: Version Number: 1.0

Version Date: 03 June 2024

Template No.: CS\_TP\_BS016 Revision 7 Reference: CS\_WI\_BS005

Page 25 of 54

For frequency tabulations and cross-tabulations, the denominator will be the number of participants per treatment arm. For tables where results are shown by analysis visit, the denominator will be the number of participants per treatment arm and analysis visit. Missing values will not be included in the denominator count when computing percentages. For cross-tabulation of post-baseline results versus baseline results, a "missing" category will be shown for baseline results, if applicable. Percentages will be presented with 1 decimal place.

Appendix 1 shows conventions for presentation of data in outputs.

## 7.3. Multiple Comparisons/ Multiplicity

No multiple comparison adjustment or alpha sharing to be considered.

## 8. DISPOSITION AND WITHDRAWALS

All participants who provide informed consent will be accounted for in this study.

## 8.1. Disposition

The number of participants will be summarized for ENR for the Final Planned Analysis (FPA). The number of participants per country and site will also be provided using the SAF for the FPA. The number of participants who completed or discontinued the treatment using the SAF, for IA and FPA and/or the study along with the reason for discontinuation will be summarized using the FAS for both the IA and FPA.

Participant disposition and withdrawals will be presented for the FAS set. Data will be tabulated at least for;

- participants each analysis sets for the FPA
- number and percentage of participants who roll over from OLE study 2104 for the FAS, IA and FPA.
- number and percentage of participants completed, or discontinued the study for the IA and FPA.
- number and percentage of participants for each study discontinuation reason or the IA and FPA.
- number and percentage of participants discontinuing treatment but continuing study assessments for the IA and FPA.

A listing of participant disposition will be prepared to present information about treatment allocation, treatment discontinuation and study discontinuation.

Document: BIOSdata\argenx\Efgartigimod\HAB40220\Biostatistics\Documentation\SAP

Author: Version Number: 1.0

Version Date: 03 June 2024

Template No.: CS\_TP\_BS016 Revision 7 Reference: CS\_WI\_BS005

Page 26 of 54

### 8.2. Protocol Deviations

- Frequency counts and percentages of participants with protocol deviations will be summarized, by class of deviations and overall using the FAS for the FPA.
- A listing will be prepared containing types of deviations and class along with additional information concerning all protocol deviations as available.

## 9. DEMOGRAPHIC AND OTHER BASELINE CHARACTERISTICS

Demographic and other baseline characteristics will be summarized using descriptive statistics for the FAS for IA and FPA.

The following demographic and other baseline characteristics will be reported for this study:

- Age (years) calculated relative to date of consent overall
  - 18-<65 years
  - 65-<75 years
  - >=75 years
- Sex
  - Childbearing potential for female subjects only
- Race
- Ethnicity
- Base line weight (kg)
- Height (cm) Measured at screening for 2104
- Baseline BMI (kg/m²)

Summary statistics including n, mean, median, SD, Q1, Q3, minimum and maximum will be presented for continuous variables such as age, height, weight, BMI and Frequency counts and percentages will be presented for categorical variables such as sex, race and ethnicity.

All demographic data and baseline characteristics will be listed.

### 9.1.Derivations

• BMI  $(kg/m^2)$  = weight (kg)/ height  $(m)^2$ 

### 10. MEDICAL HISTORY

Surgical and Medical History & Concomitant illnesses information will be presented for the SAF.

Refer to the criteria in Appendix 1 for which Surgical and Medical History collects in POTS will be added into POTS-

Document: BIOSdata\argenx\Efgartigimod\HAB40220\Biostatistics\Documentation\SAP

Author: Version Number: 1.0

Version Date: 03 June 2024

Template No.: CS\_TP\_BS016 Revision 7 Reference: CS\_WI\_BS005

Effective Date: 01Nov2021

Copyright © 2009, 2010, 2012, 2016, 2018, 2019, 2021 IQVIA. All rights reserved. The contents of this document are confidential and proprietary to IQVIA Holdings Inc. and its subsidiaries. Unauthorized use, disclosure or reproduction is strictly prohibited.

Page 27 of 54

#### OLE.

Medical History and Concomitant illnesses will be coded using the latest version of MedDRA (medical dictionary for regulatory activities).

- Medical History conditions are defined as those conditions which stop prior to or at Baseline. Hence, any
  medical history abnormalities/conditions and any event before or at Wk 24 2104 will be presented as Medical
  History.
- Concomitant illnesses which started prior to or at wk 24 2104 date and are ongoing during the study will be reported. These are also recorded in Medical History page of the eCRF.
- Medical history and concomitant illnesses will be presented by SOC and PT.

Frequency and percentage of participants with findings by SOC and PT will be presented for FPA only.

## 11. THERAPIES

All therapies will be coded using WHO-DRUG and presented for the SAF. Anatomical Therapeutic Chemical (ATC) selection is performed. ATC coding up to level 4 is available in the clinical database.

Refer to the criteria in Appendix 1 for which Prior and Concomitant Therapies collects in POTS will be added into POTS-OLE.

See Appendix 3 for handling of partial and missing dates for medications.

Based on their start dates, therapies will be allocated to 1 or both of the following categories:

- Prior therapy: the therapy strictly started before the first dose date in this 2105 study
- Concomitant therapy: the therapy was taken on or after the first dose date in this 2105 study

If the start and/or stop date is incomplete or missing, the therapy will be allocated to both categories unless the available parts of the start and/or stop date provide evidence that the therapy was not administered during the specific period.

• Prior and concomitant therapies will be tabulated by ATC class (level 1 and 3) and generic term. All prior and concomitant therapies will be listed.

### 12. STUDY MEDICATION EXPOSURE

Exposure to IMP in days will be summarized for the SAF for IA and FPA.

Document: BIOSdata\argenx\Efgartigimod\HAB40220\Biostatistics\Documentation\SAP

Author: Version Number: 1.0

Version Date: 03 June 2024

Template No.: CS TP BS016 Revision 7 Reference: CS WI BS005

Page 28 of 54

The infusion start date/time and infusion end date/time of each dose administered along with total dose administered at each visit will be recorded. The date of first study infusion will be taken from the eCRF "Exposure - Infusion" form. The date of last study infusion will be taken from the eCRF "End of Study Treatment" form. Interruptions, compliance, and dose changes are not taken into account for duration of exposure.

• As per protocol, a variation of more than 10% of the amount of 10 mg/kg will be considered an overdose. Overdosed information is as collected in "Exposure – Infusion" page of eCRF.

The total treatment administration duration, the duration on weekly infusions, two weekly infusions, and reverting back to one weekly infusion will be summarized using descriptive statistics. The Number of administrations in total, and per dosing regime will be summarized using descriptive statistics.

Compliance will be further summarized by visit for each of the three regimens. All IMP administration data will be listed. Participants with an overdose of IMP will be listed.

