## 4.2.Interim Analysis

One interim analysis will take place for this study once all the participants have completed the week 24 assessments on 2104 or discontinued the study prior to week 24. Interim analyses identified in this SAP will be performed by IQVIA Biostatistics following authorization of this SAP, database lock and analysis sets. The results of interim analysis will be based on the unblinded data. Section 9.4 of the protocol can be referred to for reference of interim analysis.

Document: BIOSdata\argenx\Efgartigimod\HAB40220\Biostatistics\Documentation\SAP

1.0 Author: Version Number:

> Version Date: 03 June 2024

Template No.: CS TP BS016 Revision 7 Reference: CS WI BS005

Page 16 of 54

Derivations and definitions for the interim analysis will be based on those required for the final analysis contained in this SAP, unless deviations are stated within the text. The list of outputs provided with the full set of output templates (planned for the final analysis) will highlight which of these outputs will also be provided for the interim analysis.

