### 12.1. Derivations

- Total treatment administration duration (days) = date of last IMP administration on specific dosing regime date of first IMP administration on specific dosing regime + 1.
- Number of administrations = Number and percentage of participants receiving 1,2,3 etc.

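### At the interim, total treatment duration is tied to the End of Study Treatment form, which participants still on treatment would not be expected to have (minor)

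*SAP*

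**What the plan says.** SAP section 12 states: "Exposure to IMP in days will be summarized for the SAF for IA and FPA". It takes the first infusion date from the Exposure - Infusion form. For the other end of the interval the source changes: "The date of last study infusion will be taken from the eCRF" End of Study Treatment form. The same paragraph confirms that dose-level dates exist: "The infusion start date/time and infusion end date/time of each dose administered along with total dose administered at each visit will be recorded".

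Section 12 lists a total administration duration as well as durations on the initial weekly, two-weekly and resumed weekly regimens. Section 12.1 gives one formula. It is labelled as total duration, but it is built from the first and last dose within a regimen ("date of last IMP administration on specific dosing regime").

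On the interim, SAP 4.2 says: "One interim analysis will take place for this study once all the participants have completed the week 24 assessments on 2104", or have discontinued before that point. It adds: "Derivations and definitions for the interim analysis will be based on those required for the final" analysis, unless the text states a deviation. Section 12 states none. SAP 7.1 leaves safety imputation to the individual sections and otherwise imputes nothing; section 12 contains no imputation rule.

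SAP 6.1 defines end of treatment as completion of treatment or permanent discontinuation of the product. SAP 15.5, on time to return to weekly dosing, censors at the earlier of last dose date and cut-off date. Section 12 has no counterpart.

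**The concern.** The rule for the last infusion date works once everyone has finished. It does not work for a participant who is mid-treatment when the interim database is cut. With no end-of-treatment record there is no last infusion date under the stated rule, and so no total duration.

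The participants who would have a duration are early stoppers and those who entered early enough to complete. The interim summary would thus be smaller and also selected: it would mix short durations from people who stopped with full-length durations from the earliest entrants, and leave out everyone in between. Safety is the primary objective and protocol 9.4 allows interims in support of regulatory interactions. Exposure is the context in which interim adverse-event counts are read, so a selective duration summary would describe that context badly.

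**Working it through.** The plan states no figure for this point, so there is none to reproduce. The check has three steps.

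**1. Will anyone be on treatment at the interim?** Planned last doses are at week 46 (day 323) on two-weekly dosing and week 47 (day 330) after a return to weekly dosing (protocol 4.1, SAP 3.1). Week 24 of the parent study is the extension baseline, so at the stated trigger the last entrant is only starting. If the trigger is instead read as week 24 of the extension, which the interim text in SAP 15.1.2 and 15.1.3 might suggest, the last entrant still has 46 − 24 = 22 weeks of dosing ahead. The answer is yes on both readings.

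**2. How many?** Inputs: about 38 participants (SAP 3.2); last dose at week 46. Assumptions: entry uniform over a span of E weeks, no dropout, and a data cut at the trigger date. The documents give no value for E, so a range is shown.

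- Stated trigger: share on treatment = 46/E (all, if E is 46 or less).
- Extension week 24: share on treatment = (46 − 24)/E = 22/E.

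| Entry span E | Stated trigger | Extension week 24 |
|---|---|---|
| 46 weeks | 46/46 = 100%, 38 | 22/46 = 48%, about 18 |
| 52 weeks | 46/52 = 88%, about 34 | 22/52 = 42%, about 16 |
| 78 weeks | 46/78 = 59%, about 22 | 22/78 = 28%, about 11 |
| 104 weeks | 46/104 = 44%, about 17 | 22/104 = 21%, about 8 |

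Dropout, or a lag between the trigger and the data cut, would lower these shares.

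**3. Which quantities use the form?** Study day = 7 × week + 1; duration = last − first + 1.

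- Always on two-weekly dosing: induction 22 − 1 + 1 = 22 days; two-weekly phase 323 − 29 + 1 = 295 days; overall 323 − 1 + 1 = 323 days.
- Illustrative return to weekly dosing with the first such dose at week 25 (day 176): two-weekly phase 169 − 29 + 1 = 141 days; resumed weekly phase 330 − 176 + 1 = 155 days; overall 330 days.

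The regimen durations need only dated infusions, which are collected. They do not add up to the overall duration: 22 + 295 = 317, against 323, because days 23 to 28 fall between regimens. Overall duration therefore cannot be had by summing regimens. It needs its own first and last dates, and section 12 sends the last one to the End of Study Treatment form.

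The remaining quantities are independent of the form. Numbers of administrations are counts of doses. Compliance uses the Exposure - Infusion page (SAP 13.1). The treatment-emergent window runs from the last administration before each event, and the follow-up time behind the event rate is the time for which events count as treatment-emergent (SAP 14.1).

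**The case against.** The best defence is that nothing is lost. Every infusion is dated and all administration data are listed, so a programmer who found the form empty would turn to the infusion records. The claim that the form is empty for ongoing participants is also an inference, because the eCRF is not shown. Both points stand. They keep this minor, but they do not remove it: the authorised text names a different source, and a programmer would have to depart from it without a documented replacement. One could use the last infusion or the cut-off date itself, and on a 14-day schedule these can differ by up to 13 days.

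A reader might infer more than the documents support, in three ways.

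- **That regimen-specific durations cannot be computed because the form holds a single date.** Section 12.1 defines them by doses on each regimen and does not mention the form.
- **That the interim safety tables lose their denominator.** The treatment-emergent window and person-time have their own dose-based definitions. Percentages of participants with events use the analysis set (SAP 7.2).
- **That exposure is missing in general.** By the final analysis all treatment has ended.

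**Conclusion.** The rule is wrong as written for one quantity at one analysis: total treatment duration at the interim. It would be summarised only for participants who had stopped or completed. This is minor, because the summary is descriptive and the dates needed are already collected.

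The size depends on an entry span that the documents do not give. For spans of 52 to 78 weeks, about 34 to 22 of 38 participants would be left out at the stated trigger, or about 16 to 11 if the interim is at extension week 24. The conclusion also rests on the inference, from the form's name and from SAP 6.1, that the form is completed only when treatment ends.

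**What to change.** In SAP section 12, take the last infusion date from the Exposure - Infusion records, as the latest infusion on or before the data cut-off. Keep the End of Study Treatment form only as a cross-check at the final analysis. In section 12.1, separate the two derivations: overall duration = last infusion − first infusion + 1 across all regimens, and the existing formula, relabelled, for each regimen.

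The cost is about two sentences in the SAP before the interim database lock. It needs no new data and no eCRF change.

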### 12.1. Derivations

- Total treatment administration duration (days) = date of last IMP administration on specific dosing regime date of first IMP administration on specific dosing regime + 1.
- Number of administrations = Number and percentage of participants receiving 1,2,3 etc.

## 13. STUDY MEDICATION COMPLIANCE

The study includes a 48-week treatment period in which all patients will initially receive QW doses of efgartigimod (10 mg/kg) by IV infusion. After 4 weeks of this induction dosing period, participants will be switched to a less frequent dosing regimen (Q2W), for the maintenance dosing period, although if clinically indicated the participant can be returned to QW dosing.

At least, the first 3 doses of IMP (at baseline, week 1 and 2 or subsequent if previous doses are missed) must be administered on-site.

The compliance will be summarized descriptively. Compliance will be further categorized as <80, 80-100, >100. All IMP administration data will be listed.

### 13.1. Derivations

Compliance is defined as: 100\* (number of doses received/number of doses expected) for each dosing regime and total. Number of doses expected will be based on participants expecting study drug infusion/administration of eCRF page "Exposure – Infusion" irrespective of dosing received. Only visits up to treatment discontinuation are considered in the compliance calculation. When a subject has reverted to weekly doses, this will be considered a separate regime

Document: BIOSdata\argenx\Efgartigimod\HAB40220\Biostatistics\Documentation\SAP

Author: Version Number: 1.0

Version Date: 03 June 2024

Template No.: CS\_TP\_BS016 Revision 7 Reference: CS\_WI\_BS005

Page 29 of 54

to the initial weekly dose regime.

#### 14. PRIMARY ANALYSIS

In order to assess the long-term safety and tolerability of efgartigimod in participants, below safety endpoints are considered within primary objective.

- Incidence and severity of AEs
- incidence of SAEs,
- changes in clinically significant laboratory test results,
- vital signs, and
- electrocardiogram (ECG) results

These endpoints will be assessed and reported based on the SAF.

#### 14.1. **Adverse Events**

AEs and SAEs will be collected as defined in the section 10.3 of the protocol. Refer to the criteria in Appendix 1 for which AEs collects in POTS will be added into POTS-OLE. AEs will be coded using latest version of Medical Dictionary for Regulatory Activities (MedDRA) central coding dictionary. AEs will be graded using the National Cancer Institute (NCI) Common Terminology Criteria for Adverse Events (CTCAE) version 5.0. For each AE, start and stop date/times are collected as well as severity, a seriousness flag, treatment-relatedness, relatedness to procedures, action taken towards the study drug and outcome.

Treatment-emergent adverse events (TEAEs) are defined as AEs with onset on or after the first administration of IMP in this 2105 study up to and including 60 days after the last IMP administration before the event (refer to schematic).

D1: IMP start	D40: Start IMP interruption		D120: IMP restart	D160: Start IMP disc			D240: Study disc		
IMP					IMP				
TE: D1-D40	TE: days	D40+60	Non-TE: 119	D101-	TE:D120-D160	TE: days	D160+60	Non-TE: >D220	

AEs will be considered treatment-emergent based on their start date/time. If the AE start date/time is incomplete or missing, the AE will be considered treatment-emergent unless the available part of the AE start or stop date/time

Document: BIOSdata\argenx\Efgartigimod\HAB40220\Biostatistics\Documentation\SAP

1.0 Version Number: Author:

> Version Date: 03 June 2024

Template No.: CS\_TP\_BS016 Revision 7 Reference: CS\_WI\_BS005

Page 30 of 54

provide evidence that the event did not occur within 60 days from last IMP administration before the event.

AE onset and duration will be calculated as follows when start and stop dates are fully known: AE onset day (vs. first administration)

- $\circ$  AE start date  $\geq$  date of first administration: AE start date date of first administration + 1 day
- AE start date < date of first administration: AE start date date of first administration
- AE duration (days) =
- AE end date -AE start date +1 day
- Study discontinuation date =
- AE start date + 1 day (when the AE start date is fully known but the AE is not resolved at the end of the study). In this case the duration will be presented as ">x days".

An AE for which the study drug was discontinued is defined as an AE with action taken "drug withdrawn".

Severity is classed as mild/moderate/severe/life-threatening/death. If a participant reports a TEAE more than once within that SOC/PT, the AE with the worst-case severity will be used in the corresponding severity summaries.

Relationship, as indicated by the Investigator, is classed as "not related" or "related". If a participant reports the same AE more than once within that SOC/ PT, the AE with the worst-case relationship to IMP will be used in the corresponding relationship summaries.

AEs leading to discontinuation of IMP will be identified by using the "Action taken with Efgartigimod/Placebo due to adverse event" from the AE page of the eCRF.

Adverse event of special interest (AESI) can be serious or nonserious, related, or unrelated to the IMP or study procedures. Infections are considered AESIs and are defined as events with a PT that falls under the MedDRA SOC 'Infections and infestations'.

Infusion/injection related reactions (IRRs) are defined as all AEs with a MedDRA PT that is listed in either:

- MedDRA Hypersensitivity SMQ broad selection
- MedDRA Anaphylactic reaction SMQ broad selection
- MedDRA Extravasation events (injections, infusions, and implants) SMQ broad selection, excluding implants and occurs within 48 hours of an infusion/injection, or within 2 days if the AE start time is not available. In case of partially missing AE start date, the AE will be considered an IRR, unless the available parts of the AE start date provide evidence it did not occur within 48 hours of an infusion/injection.

Any deaths during the study are recorded on the "Deaths Details" page of the eCRF. A death case is defined as an AE with outcome 'fatal'. Fatal events will be presented in a summary table presenting overall TEAEs and a data listing along with primary cause of death.

BIOSdata\argenx\Efgartigimod\HAB40220\Biostatistics\Documentation\SAP Document:

1.0 Author: Version Number:

> Version Date: 03 June 2024

Reference: CS WI BS005

Template No.: CS\_TP\_BS016 Revision 7

Page 31 of 54

Summary tables will only include TEAEs. However, all AEs reported during the study will be listed. Summary tables by SOC and PT will be sorted alphabetically.

An overview table of AEs will be presented to show number and percentage of participants with at least one event, and the number of events and the event rate per 100 PYFU, for the SAF at the IA and FPA for the following;

- TEAEs (IA and FPA)
- Serious TEAEs (IA and FPA)
- Grade ≥3 TEAEs (IA and FPA)
- Fatal TEAEs
- Treatment-related TEAEs according to the Principle Investigator (IA and FPA)
- Procedures-related TEAEs (FPA Only)
- Serious treatment-related TEAEs (IA and FPA)
- TEAEs leading to IMP discontinuation (IA and FPA)
- TEAEs leading to IMP interruption
- TEAEs of special interest (IA and FPA)
- IRRs (IA and FPA)

